Although there have been no known deaths in human research participants, there have been deaths in animal studies. The significance of this is unknown.

As with any drug, it is possible that participants could experience an allergic reaction to any of the drugs or combination of the drugs used in this study. Symptoms of any allergic reaction can include a rash, hives, itching, and/or difficulty breathing, closing of the throat, swelling of the lips, tongue or face, and rarely death. If participants think they are having a severe allergic reaction, they will be instructed to dial 9-1-1 and seek medical attention immediately. Patients should inform their study doctor, before signing this document, if they have ever had an allergic reaction to CBD or CBD-like products. The study medicine contains the following: CBD, Sesame oil, Ethanol, Sucralose (artificial sweetener), and strawberry flavoring. If subjects are allergic to any of these they should not take part in this study.

The study drug must be kept out of the reach of children or those with limited ability to understand.

During blood draws, participants may experience some discomfort, bruising, or temporary pain at the site of needle entry into the vein, as they might during any blood draw. There is a remote risk of fainting. Infection could occur at the place where the needle goes into the arm. However, study staff will take all available precautions to prevent an infection by using sterile technique.

The 30-60 minute EEG may cause some inconvenience to the participant because the paste or glue used to apply the electrodes onto the scalp, may get stuck in the participant's hair and require more than one shampooing to remove completely. In rare instances, the paste or glue may cause mild skin irritation. This normally will heal by itself.

In addition, there might be risks or inconveniences to participants, an embryo, a fetus, or a breast-feeding infant that are currently unforeseeable. Becoming pregnant could pose unforeseeable risks to the embryo, fetus, or breast-feeding infant.

There is also the minor risk of loss of confidentiality.

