Subjects may not take the study medication outside the country they live in as it is illegal to transport it across many international borders. Subjects cannot take part in this study if they plan to take a trip abroad during the period of the study. It is also possible that subjects may not be able to take their study medication into another state.

Food

Eating food with the medication does not affect how the study medication works for subjects.

Blood Donation

Subjects should abstain from donation of blood during the study.

Recruitment and Enrollment:

Participant Recruitment:

Epilepsy patients interested in the CBD program have been contacting our department since the Senate Bill 174 passed in April 2014. When the Alabama Senate Bill 174 was passed, a CBD phone line was established to field all calls inquiring about this research program (both adult and pediatric).

We have collected patients' names and phone numbers, per IRB personnel instruction, and created a list of interested participants. The patients were informed once additional information was available, they would be contacted by our Program Manager or study coordinator(s). Patients who have previously contacted us about participation, whether part of the PI's or Sub-I's direct clinic population or not, will be contacted using the information provided during their last contact with the Program Manager.

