- Results of routine laboratory studies, including but not limited to CBC, CMP, LFTs, renal panel, UA and levels of all AEDs within 3 months prior to submitting these records for CBD Treatment Approval Committee review. If AED dose was adjusted in the preceding 3 months, level on the new dose will need to be provided.
- Results of any metabolic or genetic testing that have been completed.

Once records are received by the study program manager, they will be forwarded to the CBD Treatment Approval Committee, via secure email, for review. Thereafter the members of the CBD Treatment Approval Committee review the patients' medical information and approve/disapprove enrollment in the study. To qualify for the study, subjects must meet all inclusion and none of the exclusion criteria based on the committee's review of their medical records. The following physicians have agreed to serve on the committee:

- [name]
- [name]
- [name]

If one of the above physicians refers their patient to the study, she or he will need to excuse herself/himself from the discussion of the Committee and [name] or [name] will serve on the Committee instead. In order for the patient to be deemed "approved" for treatment through the CBD study, all three committee members must agree the participant should be included. Once records are reviewed and the patient is deemed "approved" as a suitable study candidate, all records, along with the written decision of the CBD Treatment Approval Committee, will be referred to the study nurse coordinator. Copy of the letter will be forwarded to the treating/referring provider and to the patient. The records will be maintained by the study physician and his staff during the time the patient is enrolled in the study.

After receiving the CBD Treatment Approval Committee's decision, the study nurse coordinator will contact the patient or parent/LAR regarding participation and send the IRB approved informed assent and/or consent forms for review. Once the participant or participant's parent/LAR expresses interest in participating, the study nurse coordinator will schedule the screening and enrollment visits.

If the patient is deemed ineligible for study participation a letter from the CBD Treatment Approval Committee will be forwarded to the patient and the referring provider with an explanation as to why the patient does not qualify. Records of the disqualified patients will be kept for later IRB reporting.

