 - Use of medical marijuana or CBD based product in the past 30 days,
 - Initiation of felbamate within last 12 months,
 - Allergy to CBD or any marijuana-type products,
 - ALT >5 × ULN or AST >5 × ULN, as seen in participant's laboratory results submitted to the CBD Treatment Approval Committee for review.
 - Hemoglobin <10 or Hematocrit <30 or WBC < 2000, as seen in participant's laboratory results submitted to the CBD Treatment Approval Committee for review.
 - In Investigator's judgement, active medical condition/treatment that impacts study activities.
 - Unable to provide consent (and no LAR),

- Unable/Failure to comply with study visits/requirements and/or instructions.
- Confirmed diagnosis for Dravet Syndrome or Lennox Gastaut Syndrome that qualifies the patient for a GW Dravet Syndrome or Lennox Gastaut Syndrome randomized controlled clinical trial for which the patient is eligible pursuant to the GW clinical trial enrollment criteria unless
- (a) there is no study that is either actively open for enrollment of patients at UAB or that is expected to actively begin enrolling patients at The University of Alabama at Birmingham within two (2) months of the date on which the patient is screened for the UAB Pediatric CBD Program or UAB Adult CBD Program. Primary residence in a State different than Alabama.
- Subjects with contraindications to MRI/fMRI at 3 Tesla (e.g., metallic artifact) will not be offered participation in the optional substudy.

Other care including routine neurological care that is not related to participation in the CBD study will be provided by the patients' primary treating neurologist.

Informed Consent:

Assent and/or consent will be obtained in a quiet setting prior to the initiation of any study procedures. The patient and/or legally authorized representative (LAR) will be given opportunity to delay assent/consent until he/she has taken adequate time to read and understand the written assent/consent and discuss the study with others outside the clinic setting. Patients and/or LAR will not be consented in writing until they are able to demonstrate adequate understanding of all aspects of the study and assent/consent process. A copy of the assent and/or consent form will be given to the patient. The signed assent and/or consent form remains in the participant's study files at the clinical center.

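### The protocol's risk text says that subjects allergic to any of five named ingredients should not take part, but the exclusion list expressly covers only one of the five

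*Protocol*

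**What the plan says.** Under Risks, Side Effects, Discomforts, and Inconveniences, the protocol states: "The study medicine contains the following: CBD, Sesame oil, Ethanol, Sucralose (artificial sweetener), and strawberry flavoring". The next sentence reads: "If subjects are allergic to any of these they should not take part in this study". Just before these, the same paragraph asks for disclosure of past reactions, but only to CBD: "Patients should inform their study doctor, before signing this document, if they have ever had an allergic reaction to CBD or CBD-like products".

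Under Travel, the protocol says: "Subjects cannot take part in this study if they plan to take a trip abroad during the period of the study".

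The exclusion criteria contain one allergy item, "Allergy to CBD or any marijuana-type products", and no travel item. The nearest item concerns where the patient lives: "Primary residence in a State different than Alabama". The inclusion criteria mention neither allergy nor travel.

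Prior to Enrollment makes the listed criteria the test for approval: "subjects must meet all inclusion and none of the exclusion criteria based on the committee's review of their medical records". Enrollment Visit Procedures then checks the same criteria again.

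**The concern.** A participation rule that sits only in the risk text is easily lost when eligibility is decided from a different list. Whoever applies the exclusion criteria line by line will find allergy addressed, limited to CBD and marijuana-type products, and may reasonably take an excipient allergy to fall outside it. The risk section would keep that child out; the criteria as written would not.

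What is at stake is mainly patient safety. The risk section itself lists breathing difficulty, swelling of the throat or face and, rarely, death among the possible signs of an allergic reaction to any drug. There is a smaller analytic consequence: both the protocol's Data Analysis section and the SAP tabulate adverse events and serious adverse events, so a reaction in a child whom the risk text meant to keep out would be counted in the safety results.

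**Working it through.** No rate, sample size or error level enters this point, so the check sets the passages side by side.

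| Bar in the risk or travel text | Expressly in the exclusion list? |
|---|---|
| Allergy to CBD | Yes |
| Allergy to sesame oil | No |
| Allergy to ethanol | No |
| Allergy to sucralose | No |
| Allergy to strawberry flavoring | No |
| Planned trip abroad | No |

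Carried over: CBD allergy 1 of 1, excipient allergies 0 of 4, foreign travel 0 of 1.

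I then followed an applicant through the steps to see whether another provision expressly fills the gap.

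1. **Records sent to the Committee (Prior to Enrollment).** The list covers imaging, EEG, ECG, drug history, seizure calendar, laboratory results and residency. Neither allergy history nor travel plans is itemised. The list does include a cover letter checklist, whose contents are not shown.
2. **Phone screening (Participant Recruitment).** A script with basic entry questions is attached to the protocol but not shown. Whether it asks about allergy cannot be checked.
3. **Committee review.** The test is the listed criteria, judged on the medical records. All three members must agree.
4. **Consent.** This follows Committee approval. The request to disclose past reactions covers CBD and CBD-like products, so it has the same gap as the exclusion line, although the ingredient statement follows directly after it.
5. **Enrollment visit.** Medical history is verified, so an allergy may come to light. The criteria against which it is checked still do not name it.
6. **General exclusions.** One rests on the investigator's judgement about an active medical condition, the other on inability to comply with requirements or instructions. Neither mentions allergy or travel.
7. **After dosing.** The discontinuation list refers to allergy to the administered products. That is wider than the entry line, but it is a reason to stop, not an entry criterion.

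No step expressly supplies the missing four ingredients.

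**The case against.** The strongest reply is that the gap in wording need not become a gap in practice. Committee approval is itself an inclusion criterion and must be unanimous, so members may decline an allergic child. Medical history is verified before dosing. The risk text reads like consent wording, and the Informed Consent section withholds written consent until the family shows adequate understanding of the study, so the parents of an allergic child should learn of the advice in time. The unseen script and checklist may already put the question. All of this stands. It limits the consequence, but it leaves the two passages in disagreement.

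Several stronger readings are tempting, and the documents do not support them:

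- A reader might infer that an allergic child would automatically pass screening and be dosed. The discretionary steps above rule that out; the documents show only that no listed criterion expressly prevents it.
- A reader might infer that different sites would decide differently. The protocol describes one program, with one approval committee and one dispensing pharmacy.
- A reader might treat the allergy sentence as an absolute bar. It says should not, which is softer than the cannot used for travel.
- A reader might expect a distorted primary outcome. The named primary items are seizure worsening leading to emergency care or hospitalization, change in blood pressure or heart rate, and significant laboratory change. An allergic reaction fits none of them directly; it would enter through the toxicity grading or the general adverse-event tables. No effect on an estimate can be shown.
- A reader might give the travel bar equal weight. No comparable harm is shown. Its span is also unclear: participation is put at approximately three years, a Month 48 visit is scheduled, and no minimum stay is required.

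**Conclusion.** The inconsistency is real and lies on the face of the text. Four of the five ingredients for which the risk section advises against participation are missing from the criteria that decide eligibility. It should be corrected because it bears on safety and costs little to put right, and the existing safeguards depend on judgement or on documents that are not shown.

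The size is modest. The number of children with such an allergy, and the number who would get through the discretionary steps, cannot be derived from the documents. The conclusion assumes that the criteria are applied as written and that the unseen screening documents do not already close the gap; if they do, what remains is a mismatch of wording. The travel bar is a minor reconciliation point.

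**What to change.** Reconcile the ingredient statement in the risk section with the allergy line in the exclusion criteria so that the same allergen list appears in both places. Check that the request to disclose past reactions matches it. Confirm that the phone script and the cover letter checklist ask for the corresponding allergy history, and add the question if they do not. Which allergens the rule should cover is for the sponsor and the investigator to settle.

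Separately, reconcile the Travel paragraph with the criteria: list the bar there, or reword the paragraph if it is not meant as an entry criterion.

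The cost is a short amendment and, at most, one added screening question. The downside is that a few otherwise eligible children may be declined.

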In addition to the above compensation, patients 15 years and older who agree to participate in an optional fMRI substudy will receive \$100.00 for each visit where an fMRI procedure is performed (in addition to the compensation provided for participation in the main study).

Participants may incur costs related to travel to and from the study site for visits and parking at study site for visits. Participants will also incur costs for the required blood and urine tests that assess for side effects and toxicity levels. The participants' insurance will be billed for all blood tests and urine tests. If the insurance will not pay or the participant does not have insurance, the participant will be responsible for payment of these blood and urine tests.

Inclusion/Exclusion Criteria:

- **Inclusion criteria**

- Patients between 1 years (12 months)-18 years with drug resistant epilepsy confirmed by video EEG recording report, and
- Patient should have history of a trial of at least four drugs, including one trial of a combination of two concomitant drugs, without successful seizure control. Vagal nerve stimulation, RNS deep brain stimulation, or the ketogenic diet can be considered equivalent to a drug trial. Patient suffering from an epileptic syndrome that is known to be refractory to treatment, such as Dravet or Lennox Gastaut Syndrome, may be included after a trial of only two drugs, and
- Between 1-4 baseline anti-epileptic drugs at stable doses for a minimum of 4 weeks prior to submitting records for review by the CBD Treatment Approval Committee.
- VNS or RNS must be on stable settings for a minimum of 3 months.
- If on ketogenic diet, must be on stable ratio for a minimum of 3 months.
- Review of the following patient medical information:
 - Most recent Brain MRI report,
 - Most recent ECG report,
 - Video/EEG monitoring report confirming the diagnosis of epilepsy,
 - Evidence that the patient has failed 4 AEDs as indicated above,
 - Patient must have at least 4 clinically countable seizures per month,
 - Seizure history to include a documented history of generalized (drop, atonic, tonic clonic, and/or myoclonic) seizures, focal seizures without loss of consciousness with a motor component, focal seizures with loss of consciousness, or focal seizures with secondary generalization, complex partial seizures with a motor or tonic component, and / or altered awareness seizures,

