
(Bayley-III®)-Emotional Assessments will be completed by the parent or LAR of the participant, instead of the NIH Emotional Measures assessments.

^e Laboratory Assessments collected at Study Visit 1 will include a CMP and CBC. The study doctor may order additional laboratory testing (blood and/or urine tests) at follow up study visits to assess for side effects and toxicity. The laboratory assessments would include: CMP, CBC, Liver Functional Tests (LFTs), Urinary Analysis and any anti-epileptic drug (AED) levels). Subjects approved for the UAB CBD Open Access Program must have laboratory studies within 3 months of the committee review which include: CBC, Complete Metabolic Panel, Urine Analysis and anti-epileptic drug levels. If the subject enrolls in the program and completes the screening visit within 3 months of the required baseline laboratory studies, they are not repeated at Study Visit #1. If the subjects enrolls outside the three month window, the laboratory studies are repeated (CBC, CMP, anti-epileptic medication levels) at Visit #1. During the initial 3 months of the titration of CBD up to 25 mg/kg/day (study visit every 2 weeks), repeat laboratory studies will be done at 4-week intervals until the 6-month visit and then every 3 months (9-month and 12-month visit) and then at 6-month intervals for the duration of the study. At each visit, complete vital signs are taken and review of potential adverse events and menstrual history will be done. If there is any concern of the anti-epileptic medication interaction with CBD, additional AED levels are drawn at the study visit. Particular attention is given if the subject is currently taking valproic acid and clobazam because of potential drug interactions. A urine analysis is completed at Study Visit #1 and will be completed as needed throughout the protocol to monitor for toxicity or potential side effects. A urine analysis schedule will be added at 3-month intervals during the first year of the study and every 6 months for years 2 and 3. An ECG is obtained as part of the screening process, but will be repeated at 6 months, 12 months and then yearly while participants are enrolled in the study. The early discontinuation visit will include a CBC, CMP, UA and an ECG.

^f Patients have the option of participating in an fMRI Substudy.

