^g An EEG will be performed at the first annual (12 month) study visit. If participant has already pasted this visit, the EEG will be performed at their next study visit.

CRFs for this program were created using the NINDS common data elements CRFs and other common Epilepsy data collection resources.

Withdrawal of Participant Consent and Early Termination/Discontinuation of Study Drug:

Study participation may be discontinued for any of the following reasons:

- Administrative decision by the investigator or GW Research Ltd or Regulatory Authority.
- Subject decision to withdraw consent/assent for study.
- Withdrawal of parent/legal authorized representative consent.
- Pregnancy.
- Evidence of allergy to administered products.
- Lost to follow up
- Patient non-compliance
- Protocol deviation that is considered to potentially compromise the safety of the patient.
- In Investigator's judgement, development of active medical condition/treatment that impacts study activities.
- Intolerable adverse event as judged by study investigator and participant.
- Serious Adverse Event, which in the investigator's opinion compromises the safety of the patient.
- ALT or AST >8xULN
- ALT or AST >5xULN for more than 2 weeks
- ALT or AST >3xULN and (TBL >2xULN or INR >1.5)
- ALT or AST >3xULN with the appearance of fatigue, nausea, vomiting, right upper quadrant pain or tenderness, fever, rash, and/or eosinophilia (>5%)
- For any clinically significant (> 3 x ULN) elevation of ALT or AST in children under 21 years of age being treated with Epidiolex in an Expanded Access IND, the following laboratory measures, at minimum, should be assessed within 72 hours: repeat ALT/AST, total bilirubin, alkaline phosphatase, and GGT.
- All trial subjects with elevated LFTs should be followed until all abnormalities return to the baseline state as assessed by the investigator with AST/ALT < 3X ULN.
- If a subject has elevated LFTs (>3x ULN) and is on valproic acid the subject must stop the CBD and the LFTs must be monitored until the return to baseline state. If the subject has shown an improvement in their seizure frequency with the addition of CBD the option to "rechallenge" CBD will be at the discretion of the study PI. It would require that the subject taper off valproic acid and be on a stable dose of antiepileptic medication for 30 days prior to restarting the CBD. They would have repeat baseline labs (CBC, CMP and AED levels) prior to restarting the CBD.

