- Development of anemia with Hemoglobin <10 or Hematocrit <30 or WBC < 2000

If the subject wishes to discontinue the study drug for any reason, the subject will be seen for an early termination visit/end of study visit. The early discontinuation visit will include a CBC, CMP, UA and an ECG.

Study Design

Dosing Adjustment/Schedule:

The titration of CBD will start with a dose of 5 mg/kg/day given in two divided doses and titrated by 5 mg/kg/2 weeks up to 25 mg/kg/day; in some patients additional titration by 5mg/kg/day every 2 weeks upto 50mg/kg/day may be instituted at the discretion of the PI upon discussion with the Co-PI ([name]) Patients will be monitored for adverse events and the dose will be reduced or the titration slowed if there are dose-limiting side-effects.

For any clinically significant ($> 3 \times \text{ULN}$) elevation of ALT or AST, the following laboratory measures, at minimum, should be assessed within 72 hours: repeat ALT/AST, total bilirubin, alkaline phosphatase, and GGT.

- Epidiolex® will be discontinued in patients who have:
 - ALT or AST $>8 \times \text{ULN}$
 - ALT or AST $>5 \times \text{ULN}$ for more than 2 weeks
 - ALT or AST $>3 \times \text{ULN}$ **and** (TBL $>2 \times \text{ULN}$ **or** INR >1.5)
 - ALT or AST $>3 \times \text{ULN}$ with the appearance of fatigue, nausea, vomiting, right upper quadrant pain or tenderness, fever, rash, and/or eosinophilia ($>5\%$)

All trial subjects with elevated LFTs will be followed until all abnormalities return to the baseline state as assessed by the investigator with AST/ALT $< 3 \times \text{ULN}$.

If a subject has elevated LFTs ($>3 \times \text{ULN}$) and is on valproic acid the subject must stop the CBD and the LFTs must be monitored until the return to baseline state. If the subject has shown an improvement in their seizure frequency with the addition of CBD the option to “rechallenge” CBD will be at the discretion of the study PI. It would require that the subject taper off valproic acid and be on a stable dose of antiepileptic medication for 30 days prior to restarting the CBD. They would have repeat baseline labs (CBC, CMP and AED levels) prior to restarting the CBD.

The dose may be maintained at any point in the titration if seizures are controlled (no seizures since last medication adjustment) or there are limiting side effects, or the maximum dose is reached.

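### A child on valproate with ALT or AST above 3x and up to 5x ULN passes the entry liver limit, then must stop CBD if the value is unchanged on drug

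*Protocol*

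**What the plan says.** **Entry.** The exclusion list in Inclusion/Exclusion Criteria has one liver limit: "ALT >5 × ULN or AST >5 × ULN, as seen in participant's laboratory results" as submitted to the Approval Committee. The inclusion list allows "Between 1-4 baseline anti-epileptic drugs at stable doses for a minimum of 4 weeks". The only antiepileptic drug named as an exclusion is recently started felbamate. Valproate is allowed, and footnote e of the visit schedule expects it, asking for particular attention to it because of possible interactions.

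**On drug.** The section on withdrawal and discontinuation says: "If a subject has elevated LFTs (>3x ULN) and is on valproic acid the subject must stop the CBD". Dosing Adjustment/Schedule repeats the rule: a subject who "is on valproic acid the subject must stop the CBD and the LFTs must be monitored until the return to baseline state". A restart is at the PI's discretion and only after seizure improvement. In addition, "It would require that the subject taper off valproic acid and be on a stable dose of antiepileptic medication for 30 days".

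**Follow-up.** Children with elevated liver tests are to be "followed until all abnormalities return to the baseline state as assessed by the investigator with AST/ALT < 3X ULN".

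**Safeguards.** Under Prior to Enrollment, "all three committee members must agree the participant should be included". The exclusion list also lets the investigator keep out a child whose medical condition or treatment would affect study activities.

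The SAP does not address the point.

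**The concern.** The entry limit and the valproate stopping rule use different cut-offs on the same tests, and the stopping rule does not ask whether the value rose on treatment. By the written criteria, a child can start an investigational drug and then have to stop it for a result that was already in the entry file.

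Stopping has a cost. Dosing Adjustment/Schedule warns that abrupt withdrawal could worsen seizures, and the only written way back requires giving up valproate. In a study of safety and tolerability, a stop forced by an entry value could also be read as intolerance of CBD.

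**Working it through.** No figure in the plan needs reproducing, so the check compares the two thresholds and then works out exposure.

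**1. Overlap of the limits.** Let x be the higher of ALT and AST in multiples of ULN, for a child on valproate. Entry passes when x ≤ 5. The stopping rule applies when x > 3. Both hold when 3 < x ≤ 5.

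| x | Excluded at entry (x > 5) | Must stop on valproate (x > 3) |
|---|---|---|
| 3 | no | no |
| 4 | no | yes |
| 5 | no | yes |
| above 5 | yes | yes |

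The stopping rule says LFTs without defining them. The neighbouring rules use ALT and AST, so the comparison is made on those.

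**2. Is the mismatch specific to valproate?** For other children, the sustained-elevation rule stops CBD above 5x ULN for more than two weeks, which agrees with the 5x entry limit. The general rules that start at 3x also need raised bilirubin or INR, or symptoms. The hemoglobin, hematocrit and WBC limits are the same at entry and at discontinuation. The valproate rule is the one that acts on a value above 3x alone.

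**3. Follow-up target.** A child who enters at 4x and returns to baseline is at 4x. The target also requires a value below 3x, so going back to baseline does not meet it.

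**4. When the value is next seen.** The Protocol conflicts on whether a chemistry panel (CMP) is drawn at Visit 1. Footnote e begins "Laboratory Assessments collected at Study Visit 1 will include a CMP and CBC", and the Study Visit 1/Day 0 list agrees. A later sentence of footnote e and Enrollment Visit Procedures say that baseline tests less than three months old at screening are not repeated. Without a Visit 1 panel, the first scheduled on-drug CMP is at Study Visit 3, Day 28, although the study doctor may order one sooner.

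**5. Exposure before the Day 28 panel.** The inputs are the doses in Dosing Adjustment/Schedule: 5 mg/kg/day in weeks 1-2, and 10 mg/kg/day in weeks 3-4 if judged appropriate.

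- Increase given at Day 14: 14 × 5 + 14 × 10 = 210 mg/kg.
- Increase withheld: 28 × 5 = 140 mg/kg.
- Visit 3 window of ±3 days (Day 25 to Day 31), with the increase at Day 14: 14 × 5 + 11 × 10 = 180 to 14 × 5 + 17 × 10 = 240 mg/kg.
- Same window, no increase: 25 × 5 = 125 to 31 × 5 = 155 mg/kg.
- If the Visit 2 window is used as well, an increase at Day 11 with the panel at Day 31 gives 11 × 5 + 20 × 10 = 255 mg/kg.

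If a Visit 1 panel is drawn and acted on before dispensing, exposure is 0 mg/kg. None of these figures includes a taper after the decision to stop.

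**The case against.** The strongest reply is that the stopping rule was meant for a rise on treatment. It sits among the discontinuation and dosing rules and speaks of a return to baseline and of rechallenge. The follow-up sentence pairs baseline with a value below 3x, which assumes that children start below 3x. That is probably the intent, but it is not written. The blood-count rule in the discontinuation list is worded as the development of anemia, so a new-onset condition was written there. The valproate rule has none.

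A second reply is that the Committee sees liver results and drug levels together, must be unanimous, and would notice a child on valproate at 4x. The investigator can also exclude on judgement. These are real safeguards, but neither gives a number, and the one number the exclusion criteria do give accepts 4x.

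A third reply is that no harm has been shown. This stands in part. The number affected is unknown, cumulative mg/kg measures exposure and not injury, and the exposure figures depend on no Visit 1 panel and no early test. The introduction to the discontinuation list is permissive, but that does not soften the rule, because the dosing section repeats it in mandatory terms.

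**Conclusion.** The inconsistency is real and exactly bounded: children on valproate with ALT or AST above 3x and up to and including 5x ULN. Whether any such child was or will be enrolled cannot be told from the documents, which give neither the share on valproate nor the distribution of baseline enzymes. Exposure before the forced stop ranges from zero, if a Visit 1 panel is drawn and acted on, to about 140-210 mg/kg at Day 28 without one. It is 125-240 mg/kg with the Visit 3 window, or up to 255 mg/kg if Visit 2 is also early. This assumes that the enzyme value stays above 3x and that the rule is applied as written.

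This is a narrow drafting gap that is worth closing because closing it is cheap. It does not threaten the analysis. The SAP reports 89 children already enrolled, so the benefit is mainly for further enrolment, which the Protocol says may be approved.

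**What to change.** Add one line to the exclusion criteria: a patient on valproic acid whose submitted ALT or AST is above 3x ULN is excluded, or deferred until the value is 3x ULN or below or valproate has been changed. For submitted values this empties the overlap.

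The cost is one line of amendment and delayed entry for perhaps a few children. No test is added, because liver results and drug levels already go to the Committee.

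The line does not cover a value that rises above 3x between submission and first dose. That depends on settling separately whether a Visit 1 panel is always drawn.

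If the investigators meant only a rise on treatment, they could instead write that condition into the stopping rule in both places. That removes the contradiction without narrowing access, but it keeps children on valproate and CBD at enzyme levels where the present rule says stop. The entry line is the more cautious choice.
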